There are a number of critical limitations in the extant literature that must be addressed if scientists are to influence the regulation of marijuana. First and foremost, scientists need to understand the effects of commonly used marijuana strains, **as they are used in every day life**, as opposed to relying solely on testing the effects of government grown marijuana in controlled laboratory experiments. This information is critical for making recommendation about how to reduce the potential for harmful use of marijuana. For example, cannabidiol (CBD) appears to mitigate some of the effects of tetrahydrocannabinol (THC), and the ratio of CBD to THC may have a large impact on the effects of the marijuana, which in turn may have important implications for harm reduction. To that end, the overarching objective of this program of research is to advance a more nuanced understanding of the potential harm associated with different strains of marijuana, using a naturalistic design with high external validity, thereby avoiding many of the pitfalls and limitations of previous research. **To that end, regular marijuana users who normally use marijuana with a THC potency of ~18% will be asked to either continue to smoke or ingest normal marijuana or switch to a strain that is theoretically less harmful (i.e., has less THC and/or more CBD).** The information gained from this research will inform the public about the potential harms of different cannabinoids and strains. It may also have a translational application with respect to identifying THC levels or CBD:THC ratios that could be the focus of future regulatory actions.

1. The first specific aim will examine cannabis products that differ markedly on THC potency (low, medium, or high: i.e. 6%, 12%, 18% THC for smoked flower and low, medium, and high: i.e. ranging from less than 2.5mg to greater than 10mg THC for edibles) but do not differ on the potency of other major cannabinoids (< .5%) to determine whether the level of THC in the product is associated with increased intoxication and greater harmful effects using a naturalistic design.

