### **Overview and Design of Study 1 (e.g., Aim 1, Hypotheses 1 and 2).**

Study 1 is designed to test the hypothesis that a high THC strain of marijuana will be associated with greater blood levels of THC and greater harmful effects, as compared to a lower THC strain, when used in a

naturalistic environment. To that end, regular flower marijuana users, who, according to our preliminary data, typically use marijuana with a THC potency of ~18%, will be assigned to use one of three strains with no CBD but with different THC potencies (low, medium, or high: e.g. 6%, 12%, or 18% THC for smoked flower) and regular edible marijuana users who typically purchase 10 mg products will be allowed to use as they normally would (producing naturally occurring low, medium, and high groups: e.g. less than 2.5mg to greater than 10 mg THC n=33 per group) for five days prior to participating in the experimental session. Measures will be collected at Appointment 1: (Baseline/**Session 1**), after 5 days of using the assigned strain, but in a sober condition before use in our mobile laboratory at Appointment 2: (**Session 2**), they will then return to their home to use the assigned strain and return to the mobile laboratory (**Session 3**), and 60 minutes after their last use at home (**Session 4**). Details regarding sample ascertainment, marijuana administration, timing of measures to be collected, power analyses, and the analytic plan for Study 1 follow. Thus, Study 1 will involve a 3 Cannabis strains: high, medium, and low THC x 4 (Time: 1, 2, 3, 4) mixed factorial design.

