### **Marijuana Administration at Home.**

Unlike other studies done in the United States to date, the proposed work will utilize a design that is observational but contains some experimental elements. Specifically, at the end of Appointment 1 (Baseline/Session 1) participants will be given instructions to purchase 3 grams of either a normally high THC strain, a medium THC strain, or a low THC strain at a dispensary (The Farm) in Boulder, Colorado. The normally high THC smoked flower strain contains 18% THC and 0% CBD and edibles can range from a low of 2.5 mg to greater than 10 mg of THC and 0 mg of CBD. **Please note the term “high” is relative given that the average potency in Colorado exceeds 18% and edibles are normally packaged in 10 mg THC doses.** The medium flower strain contains 12% THC and 0% CBD. The low flower THC strain contains 6% THC and 0% CBD. Colorado requires all strains of flower and edibles to be tested by a state licensed lab, which allows us to have a precise measure of potency to operationalize our high, medium, and low THC strains. Furthermore, the dispensary that we will work with (The Farm - see letter of support) performs cannabinoid and terpene potency testing on each batch produced. The dispensary will set aside a specific lot of the strains which will be labeled as “Strain A”, “Strain B”, and “Strain C” such that participants, dispensary staff, and research staff will be blind to which strain was purchased. Thus, 3 grams of each marijuana strain will be packaged in childproof bottles labeled as “Strain A”, “Strain B”, and “Strain C.” Our preliminary data suggests that 3 grams is sufficient for the study. [name] (co-investigator) will maintain the blind. The instruction to purchase “A” or

“B” or “C” will be urn randomized across participants such that equal numbers of male and female participants are included in the high, medium, and low conditions. The observational aspect of the design involves the instruction that participants can use as little or as much of the marijuana as they wish during the five days prior to the experimental appointment. The five-day period allows each participant to become accustomed to the strain. Subjects are prompted by email or text message to report how much was used each day using an online reporting system. On the fifth day, the research assistant calls the participant one hour prior to their appointment to remind the participant about the upcoming appointment from the research team.

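### Edible users are to form three potency groups of 33, but nothing in the design fills those groups and the passages defining them conflict

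*Protocol*

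**What the plan says.** Study 1 compares three THC levels in a group-by-time design (Protocol, section IV, Overview and Design of Study 1). Flower users are randomised to 6%, 12% or 18% THC. Edible users are not assigned a product: the overview takes 10 mg as their typical purchase and leaves their use unchanged. It describes the result as "producing naturally occurring low, medium, and high groups: e.g. less than 2.5mg to greater than 10 mg THC n=33 per group".

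The edible levels appear in two other places. Specific Aim 1 (section I, Objectives) gives them as "ranging from less than 2.5mg to greater than 10mg THC for edibles". Section IV, Marijuana Administration at Home, says "edibles can range from a low of 2.5 mg to greater than 10 mg of THC and 0 mg of CBD" and adds that "edibles are normally packaged in 10 mg THC doses". That section also says that state testing of flower and edibles "allows us to have a precise measure of potency to operationalize our high, medium, and low THC strains".

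On intake, the same section says that "participants can use as little or as much of the marijuana as they wish during the five days", and that "Subjects are prompted by email or text message to report how much was used each day using an online reporting system".

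The power analysis (section IV) assumes 99 participants in three groups of 33, four assessments, a correlation of .60 and an interaction effect of f = .12. It does not separate flower from edibles.

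**The concern.** A group size can be planned when the investigator assigns the groups or recruits to a quota. Neither is described for edible users, yet a size of 33 per group is stated. If usual use clusters at one product strength, most edible users fall in one class and the outer classes are small.

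The definition of the classes is also unsettled, in three respects: where the low end lies, where the typical product falls, and whether the class describes the product bought or the amount eaten.

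Hypothesis 1 is most exposed. There the group is the predictor and blood THC is the outcome. If the edible groups are badly formed or very unequal, a null result for edibles could reflect the grouping and say little about THC.

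**Working it through.** **1. The passages side by side.**

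| Point | One place | Another place | Result |
|---|---|---|---|
| Low end | Aim 1 and design overview: below 2.5 mg | Administration at Home: lowest edible is 2.5 mg | By product content, nothing listed lies below 2.5 mg |
| Typical product | Design overview and Administration at Home: 10 mg | Aim 1 and design overview: upper end is above 10 mg | 10 is not above 10, so the typical edible is not at the upper end |
| Meaning of high, flower | Typical flower is about 18% | High flower strain is 18% | High means typical for flower but above typical for edibles |
| Basis of the class | Aim 1 and the potency-testing sentence point to product content | Groups arise from usual use, with no limit on amount | Basis not stated |

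The last row matters because one, two or three 10 mg units give 10, 20 or 30 mg. Product content is the same in all three cases, but intake differs up to three-fold.

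**2. The plan's own power figure.** Inputs from the power analysis section: N = 99, g = 3 groups, m = 4 assessments, ρ = .60, f = .12, two-tailed α = .05. For the within-between interaction, with sphericity (ε = 1):

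- λ = f² × N × m / (1 − ρ) = 0.0144 × 99 × 4 / 0.40 = 14.256
- df1 = (g − 1)(m − 1) = 6; df2 = (N − g)(m − 1) = 288
- power = .811

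The stated figure therefore reproduces, for equal groups.

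**3. Would 33 arise without a quota?** The protocol gives no distribution of edible doses, so the natural share of an outer group is an assumption and is varied. The chance that at least 33 of 99 edible users fall in one given outer group (binomial) is:

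| Assumed share | Chance of at least 33 of 99 | Edible users needed to expect 33 (33 / share) |
|---|---|---|
| 33.3% | .54 | 99 |
| 30% | .27 | 110 |
| 25% | .039 | 132 |
| 20% | .0013 | 165 |
| 10% | 2 × 10⁻¹⁰ | 330 |

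**4. Power with unequal groups (illustration).** Suppose all 99 were edible users and the effect keeps the same linear pattern (−1, 0, +1). With share q in each outer group, the between-group variance of the pattern is 2q, against 2/3 in equal groups. So f = .12 × √(3q) and λ = 14.256 × 3q. The standard error of the high-low difference, relative to plan, is √[(2/(99q)) / (2/33)] = √(1/(3q)).

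| q | Group sizes | f | λ | Power | SE ratio |
|---|---|---|---|---|---|
| 1/3 | 33 / 33 / 33 | .120 | 14.26 | .81 | 1.0 |
| .20 | 19.8 / 59.4 / 19.8 | .093 | 8.55 | .55 | 1.3 |
| .10 | 9.9 / 79.2 / 9.9 | .066 | 4.28 | .28 | 1.8 |
| .05 | 5.0 / 89.1 / 5.0 | .047 | 2.14 | .15 | 2.6 |

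**The case against.** The strongest reply is that the protocol fixes no cut-offs. Both places give a span running from below 2.5 mg to above 10 mg, the design overview only as an example, and no boundary for the medium group appears anywhere. Exact boundaries can be left to an analysis plan. This stands. A reader might infer a rule of below 2.5, 2.5 to 10 and above 10 mg, under which products of 2.5, 5 and 10 mg would all be medium, but that rule is not in the document.

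A reader might also infer that the three groups cannot form. The text does not support that. If the class follows amount eaten, part of a unit can fall below 2.5 mg and two units of 10 mg exceed 10 mg. Nor is it shown that a product label misstates the dose in the planned analysis, because grouping edible users by label is suggested but not stated.

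Finally, the protocol admits its limited control over use and relies on blood THC as the objective dose measure. For Hypothesis 2, blood THC replaces group as the predictor if group differences turn out to be few. That is a real safeguard for Hypothesis 2. It does not help Hypothesis 1, where blood THC is the outcome and cannot stand in for the group.

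What the reply leaves untouched is the stated 33 per group for unassigned participants, the mismatch at 2.5 mg, and the unstated basis of the class. The first two are in the protocol's own text, and the third is needed before any boundary can be applied.

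**Conclusion.** The point holds in this form. For edible users the protocol states a group size that its design does not secure, and it describes the groups inconsistently. Equal groups are not assured and are unlikely if most use is at 10 mg, so the power of .81 does not carry over to an edible comparison.

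The size of the loss is not known. The figures of .55, .28 and .15 rest on assumed outer shares of 20%, 10% and 5%, on a linear pattern, and on all 99 participants being edible users. They show how sensitive the design is and do not predict what will happen. It is also unclear whether 33 per group covers edibles alone or both forms together: 33 per group in each form would need 2 × 99 = 198 participants, against the 99 stated.

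The power calculation itself is correct for the equal groups that it assumes.

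**What to change.** - Reconcile the three descriptions of the edible levels (Aim 1, design overview, Administration at Home). State whether the edible measure is product content or amount eaten. No dose boundary is proposed here.
- Withdraw the 33 per group for edible users, or restate it as an expectation that is not assured. Say how many of the 99 are to be edible users.
- For edible users, replace the three-class factor in Hypothesis 1 with mg THC consumed (tested content × amount eaten) as a continuous predictor. Use observed tertiles for display only.
- Record the product and the amount eaten at home immediately before Session 3. The instrument table in section XII lists nothing at Session 3 that asks for this, and it is the use that drives Times 3 and 4.

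The cost is some wording and one added question, since tested content and daily amounts are already planned. There are two drawbacks: amount eaten is self-reported, and the edible result becomes a dose-response slope that does not line up with the three flower classes. As the edible users are not randomised, that slope is an association.

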### **Participant Recruitment and Selection.**

Recruitment to date has primarily come from flyers, business cards, and announcements placed in dispensaries in Boulder. With our new approach that involves driving the mobile lab to the participants' location, we will be able to broaden our catchment area. Interested participants will be asked to call the lab. The study technician will then screen the participant according to the inclusion criteria below. If the participant meets inclusion criteria, he or she will be scheduled for the next available appointment to complete informed consent and baseline measures. Participants will be instructed not to drink alcohol within 24 hours of the appointment, or consume caffeine for one hour prior to the appointment (note: individuals who smoke tobacco daily, consume alcohol more than 2x per week (and 3 or more drinks per occasion), or use other illicit or prescription drugs are excluded). It is important to note that dispensaries in Boulder attract customers who are diverse in age, sociodemographic status, gender, and race. In addition, we exclude University of Colorado students and employees for legal reasons, which has the added benefit of resulting in a more diverse sample. Thus, men and women of all ethnic backgrounds will be recruited into the study. We expect that the sample will reflect the diversity of Boulder/Denver area of Boulder, such that approximately 35% of the final sample will represent Latino and non-Caucasian individuals.

### **Marijuana Administration at Home.**

Unlike other studies done in the United States to date, the proposed work will utilize a design that is observational but contains some experimental elements. Specifically, at the end of Appointment 1 (Baseline/Session 1) participants will be given instructions to purchase 3 grams of either a normally high THC strain, a medium THC strain, or a low THC strain at a dispensary (The Farm) in Boulder, Colorado. The normally high THC smoked flower strain contains 18% THC and 0% CBD and edibles can range from a low of 2.5 mg to greater than 10 mg of THC and 0 mg of CBD. **Please note the term “high” is relative given that the average potency in Colorado exceeds 18% and edibles are normally packaged in 10 mg THC doses.** The medium flower strain contains 12% THC and 0% CBD. The low flower THC strain contains 6% THC and 0% CBD. Colorado requires all strains of flower and edibles to be tested by a state licensed lab, which allows us to have a precise measure of potency to operationalize our high, medium, and low THC strains. Furthermore, the dispensary that we will work with (The Farm - see letter of support) performs cannabinoid and terpene potency testing on each batch produced. The dispensary will set aside a specific lot of the strains which will be labeled as “Strain A”, “Strain B”, and “Strain C” such that participants, dispensary staff, and research staff will be blind to which strain was purchased. Thus, 3 grams of each marijuana strain will be packaged in childproof bottles labeled as “Strain A”, “Strain B”, and “Strain C.” Our preliminary data suggests that 3 grams is sufficient for the study. [name] (co-investigator) will maintain the blind. The instruction to purchase “A” or

“B” or “C” will be urn randomized across participants such that equal numbers of male and female participants are included in the high, medium, and low conditions. The observational aspect of the design involves the instruction that participants can use as little or as much of the marijuana as they wish during the five days prior to the experimental appointment. The five-day period allows each participant to become accustomed to the strain. Subjects are prompted by email or text message to report how much was used each day using an online reporting system. On the fifth day, the research assistant calls the participant one hour prior to their appointment to remind the participant about the upcoming appointment from the research team.

After consulting with CU legal counsel, we now plan to utilize a mobile lab, which will facilitate blood and data collection on site, rather than transporting the subjects to the lab for assessments as we did in our preliminary study. The mobile lab will be based on the Dodge/Mercedes Sprinter van platform (see pictures) with comfortable seating and space for blood draws and cognitive testing on laptops. This change addresses potential problems, like the variable (10 - 20 minute) delay between the time the individual uses the marijuana and the time we can collect the first blood sample, self-report, and cognitive data. This change also addresses concerns with how feasible it is to recruit a sufficient number of subjects within a short driving radius of the lab. There are other advantages; the mobile lab will be outfitted in a comfortable, lounge-like atmosphere with appropriate décor (i.e., glassware and artwork found in dispensaries). This is consistent with the reviewer’s suggestion to create a more naturalistic environment for the assessments. Thus, rather than bring the subject to the lab as we did in the preliminary study, the RA and phlebotomist will travel to the location of each participant. The subject will use the strain in the privacy of their home, and then walk to the mobile lounge lab. The phlebotomist will immediately draw blood and the RA will begin assessments. At the end of the appointment, the subject will be compensated and escorted back to their home.

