### **Assessment of Compliance.**

We ask participants to bring the receipt from the dispensary to verify which strain was purchased, and the RA visually confirms the label (e.g., A, B, or C) at the experimental session.

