Then they will return to the mobile laboratory for Session 3, where a blood draw self-report measures, and the cognitive battery will be collected in the mobile lab. The blood draw (22 ml), questionnaires and cognitive battery will be repeated at 1 hour after Session 3 at the mobile lab (Session 4). After the last assessment, the participant will be paid \$150 to compensate them for their time and effort (Appointment 1: \$50 for Session 1, Appointment 2: \$50 for Session 2, \$25 for Session 3, \$25 for Session 4), debriefed, and escorted back to their home.

Name of instrument/tool/procedure	Purpose (i.e. what data is being collected?)	Time to Complete
Appointment 1: Baseline/Session 1		
Urine Testing	
 
A urine sample will test for illicit drugs other than marijuana (e.g. cocaine, benzodiazepines, opiates, MDMA, sedatives, or methamphetamine).
 
	
Pregnancy Screening	
 
All female participants will take a urine pregnancy test.
 
	
Demographics Questionnaire	
 
Age, sex, marital status, race/ethnicity, SES, occupation, income, education, and religious affiliation.
 
	
Alcohol Use History Questionnaire	
 
Targets the frequency of lifetime and recent use for alcohol.
 
	
Pain Intensity	
 
Consists of one item asking about the participant's level of pain in the past seven days. Participants are asked to rate their pain on a scale from 0 (no pain) to 10 (worst imaginable pain).
 
	
Promis Pain Interference CAT	
 
This asks participants about how their experience of pain interfered with or affected their enjoyment of various daily activities in the past seven days. The scale is computer-adapted and has a minimum of four questions and a maximum of 12 questions. The questions ask for a response on a 5-point scale. Some of the items are rated: Not at all; A little bit; Somewhat; Quite a bit; Very much; other items are rated: Never; Rarely; Sometimes; Often; Always.
 
	
Health Related Quality of Life	
 
This is a Short Form 36 Health Survey, which consists of 36 questions across nine health domains and is sensitive in detecting changes over time in health-related quality of life.
 
	

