The Pittsburgh Sleep Quality Index (PSQI)	
 
The Pittsburgh Sleep Quality Index (PSQI) is an effective instrument used to measure the quality and patterns of sleep. It differentiates “poor” from “good” sleep by measuring seven domains: subjective sleep quality, sleep latency, sleep duration, habitual sleep efficiency, sleep disturbances, use of sleep medication, and daytime dysfunction over the last month. The client self rates each of these seven areas of sleep
 
	
Cold Presser Task	
 
Participants immerse their hand in cold liquid and withdraw their hand from the liquid (pain tolerance) and the timing is recorded. There is a risk of discomfort.
 
	
Session 2 & 3		
Exercise Cognitions	
 
This measure will be used to examine the acute cognitive effects of cannabis consumption on participants’ exercise cognitions, specifically exercise intentions, motivation, and self-efficacy. These measures are slight variations of assessments of exercise cognitions used in our prior work (Bryan & Rocheleau, 2002).
 
	
Session 3 & 4		
The Drugs Effects Questionnaire (DEQ)	
 
The Drug Effects Questionnaire (DEQ) is a 5 items visual analog scale used to measure the strength of marijuana as well as the desirable effects (de Wit & Phillips, 2012).
 
	
The Addiction Research Center Inventory	
 
The Addiction Research Center Inventory (ARCI; Martin, Sloan, Sapira, & Jasinski, 1971), including the ARCI—Marijuana (M) scale (Chait, Fischman, & Schuster, 1985) will be used to measure subjective effects of marijuana in addition to drug-induced euphoria, stimulant-like effects, intellectual efficiency and energy, sedation, dysphoria, and other somatic effects.
 
	
Session 4		
Cold Presser Task		

 
Participants immerse their hand in
 
		

cold liquid and withdraw their hand from the liquid (pain tolerance) and the timing is recorded. There is a risk of discomfort.		
Assessment of Blind and Potency of Marijuana	
 
At the end of the experimental session, participants will be asked to guess which strain they received and to guess the potency of THC and CBD in that strain.
 
	

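### One fixed letter per strain serves every randomised flower participant and the outcome assessor sees it, so one decoded letter unblinds an arm and a second unblinds all three

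*Protocol*

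**What the plan says.** Under Marijuana Administration at Home (section IV), three flower strains of 6%, 12% and 18% THC are bought at one named dispensary. On coding, "The dispensary will set aside a specific lot of the strains which will be labeled as" Strain A, B and C, with the stated aim that "participants, dispensary staff, and research staff will be blind to which strain was purchased". A co-investigator maintains the blind. Urn randomisation decides which letter a participant is told to buy. No section describes numbered bottles, rotating codes or several codes per strain.

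Assessment of Compliance sets out two checks. The first concerns the purchase: "We ask participants to bring the receipt from the dispensary to verify which strain was purchased". The second puts the letter itself in front of a member of staff: "the RA visually confirms the label (e.g., A, B, or C) at the experimental session".

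On staffing of the mobile laboratory, "the RA and phlebotomist will travel to the location of each participant". Once the participant comes back after use, "The phlebotomist will immediately draw blood and the RA will begin assessments".

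In the measures table of section XII, at the end of Session 4, "participants will be asked to guess which strain they received and to guess the potency of THC and CBD in that strain". After the last assessment the participant is paid, "debriefed, and escorted back to their home". Neither the table nor the text says who collects the guess or who debriefs.

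The overview of Study 1 lets regular edible users continue their usual use, so no letter defines their groups.

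**The concern.** With one letter per arm, the letter is itself the treatment code. Every participant's reaction or guess is evidence about all others with the same letter, past and future. Three features make it plausible that a letter could be worked out:

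- Participants must not currently use a strain below 18% THC (inclusion criterion 4), while the low strain is 6%, a threefold difference. They use it at will for five days before the experimental session.
- Everyone buys at the same dispensary, so talk about a letter can reach later participants.
- The RA sees the letter, sees the participant after use and begins the assessments, so impressions can build up by letter.

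A participant or assessor who believes a strain is strong or weak may shift DEQ ratings or the conduct of an assessment in the hypothesised direction. This matters most if Hypothesis 2 is tested by randomised group, the route the protocol takes when Hypothesis 1 shows group differences in blood THC. Because use is ad libitum, such a belief could also change how much is taken, which would touch blood THC indirectly.

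**Working it through.** **1. What a decoded letter reveals.** Inputs: three letters and three strains (Marijuana Administration at Home); about 111 recruited, 37 per group (The impact of attrition). The recruitment figure follows from the protocol's own inputs: 33 / 0.9 = 36.7, rounded up to 37 per group, and 3 × 37 = 111. I assume all 111 are randomised flower participants. If edible users are counted among them, each lettered arm is smaller but the fractions are unchanged.

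- Possible keys: 3! = 6, so a blind guess at the whole key is right with probability 1/6 = .17.
- One letter known: 2! = 2 keys remain. That arm, 37 / 111 = 33%, is identified. The other 74 are a 50/50 choice between two strains.
- Two letters known: 1 key remains, and all 111 are identified.

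**2. Who holds which information.** The compliance section gives the RA the letter, and the mobile-laboratory text has the RA begin the assessments. That overlap is explicit. Any link between the letter, the end-of-session guess and the debriefing in one person's hands is not, because no role is named for the last two.

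**3. How fast pooled guesses would reveal the key.** The protocol gives no guess accuracy, so it is varied here as an assumption. Model: n guesses per letter, each correct with probability p, errors split equally between the other two strains. The key chosen is the one of the six with the most matching guesses, ties broken at random. There were 20,000 simulated trials per cell. Probability that the full key is right:

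| Correct guesses | n = 5 per letter | n = 10 | n = 20 | n = 33 |
|---|---|---|---|---|
| 1/3 (chance) | .17 | .17 | .17 | .16 |
| 40% | .32 | .39 | .50 | .61 |
| 50% | .59 | .76 | .91 | .98 |
| 60% | .82 | .95 | >.99 | >.99 |

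Identifying one given letter, such as that of the low strain, is easier. After 10 per letter the probability is about .54, .83 and .97 at 40%, 50% and 60% correct (chance .33).

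These figures describe an observer who sees every guess with its letter and pools them optimally, so they are an upper bound on what guesses alone would reveal to staff.

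**The case against.** **Stronger readings that the protocol does not support.**

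- A reader might infer that the whole trial is unblinded as soon as one letter is known. With three arms, one letter identifies a third and leaves the rest at 50/50.
- A reader might infer that the person who checks the letter also debriefs and hears the guess. That is likely, since the RA and phlebotomist are the staff described as travelling to the participant, but no role is named. The stored data are described as coming from survey software (section XIV), so the guess may already be entered privately. Nothing says that the strain is revealed at debriefing or in an emergency.
- A reader might infer that the protocol's claim of high internal validity for the group comparison rests on the blind. The text credits random assignment.
- A reader might conclude that half the sample will be assessed with the key known. The protocol says users may titrate to a desired level, which could bring guesses close to chance. At 35% correct the full key is recovered with probability only about .2 after 10 per letter. At 50% it takes 20 per letter, or 60 of 111 participants, to reach .91. No section describes the pooling that these figures assume.

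**Other points against.** The guess follows that participant's own assessments, so giving it cannot bias them; the harm is carry-over to later participants. Blood THC is a laboratory measure, and cognitive testing is on laptops. The guess itself lets the team see whether the blind failed. Numbered bottles would not stop an experienced user noticing a weak product.

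All of this narrows the point. It does not answer the central one: the codes are shared across each arm, and the assessor is shown them.

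**Conclusion.** The concern holds in limited form. The protocol fixes one letter per strain for all randomised flower participants and lets the RA who begins the assessments see it. Once a letter is worked out, that arm, about 37 of 111, is open for every later assessment; a second letter opens all three. The exposure is mainly to DEQ ratings and RA-run assessments under Hypothesis 2.

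The structural part follows from the text alone. The speed of leakage does not: it rests on an assumed guess accuracy and on pooling of guesses, and ranges from slow at 40% correct to rapid at 60%. The sample size and power figures are unaffected. This is a cheap improvement to the blind and does not show that the blind will fail.

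**What to change.** - In Marijuana Administration at Home, replace the three letters with a unique bottle number per participant, or at least many codes per strain. The number-to-strain list should be held only by the co-investigator who already maintains the blind.
- In Assessment of Compliance, have the receipt and label check confirm the assigned number.
- In the Session 4 procedures, have the participant enter the strain and potency guess on the laptop, unseen by the RA. State that no strain is disclosed at debriefing until data collection has closed.

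The cost is about 111 numbered labels, a code list, and a dispensary that must hand over a specific bottle instead of any bottle of a given letter. No extra staff, visits or participants are needed. The change removes carry-over between participants but leaves each participant's own perception of potency, so the end-of-session guess should be kept.
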